	
As a results of the COVID-19 pandemic, temporary changes to the protocol have been implemented. These changes are described in Appendix 14. Patients who are not experiencing severe side-effects, or have deteriorated significantly while on the treatment and provide informed consent will be eligible to continue treatment for an additional 6 months in a double-blind, placebo-controlled extension treatment period (or longer, in case a patient is willing to be enrolled in the open-label study IEDAT-03-2018, but the study has not yet received IRB/EC approval at the time the patient reaches Visit 15/Month 12). Patients meeting all entry criteria will be treated as follows:
 
 • Patients originally randomized to EDS-EP treatment groups (Group 1 or Group 2) will continue on the same treatment; • Patients originally randomized to the Placebo group (Group 3) will be re-randomized in equal proportions (1:1) to receive either the EDS-EP ~5-10 mg DSP/infusion or ~14-22 mg DSP/infusion, as follows: 
 ○ Following 6 months of treatment, one third of the originally randomized placebo patients will be re-randomized to treatment with EDS-EP, as described above; ○ After 9 months of treatment, one third of the originally randomized placebo patients will be re-randomized to treatment with EDS-EP, as described above; ○ At 12 months, all remaining placebo patients who continue open-label treatment will receive treatment with EDS-EP, as described above. 
The ICARS will be administered by a site rater and scoring verified by a central remote qualified rater, based on a video recording of the assessment at the site. The scores provided by the central remote raters will be used for the primary analysis of the ‘Modified’ ICARS (primary efficacy endpoint). The site ICARS rater will not be involved in the rating of the CGI-S and CGI-C, VABS, QoL or A-T NEST scale. The CGI rater will not have access to the ICARS ratings, but may refer to other scales in scoring the CGI.
 
All patients who complete 12 months of treatment in the trial, complete the study assessments, and provide informed consent will be eligible to continue treatment with EDS-EP in an open-label, extension study (IEDAT-03-2018). In case a patient is willing to be enrolled in the open-label study IEDAT-03-2018, but the study has not yet received IRB/EC approval at the time the patient reaches Visit 15/Month 12, the patient may undergo unscheduled monthly assessments/infusions (according to the assigned blinded treatment) starting from the time Visit 15/Month 12 should be performed, and continuing until the site has been initiated for the open-label study IEDAT-03-2018 and he/she has been evaluated for eligibility for the study. All patients, including those previously treated with placebo, who meet all of the selection criteria will receive monthly infusions of EDS-EP (dose range of ~14-22 mg DSP/infusion).

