
Investigational Medicinal Product(s): dose, mode of administration, and dosing schedule
	
The study treatment consists of one of two dose ranges of dexamethasone sodium phosphate (DSP) administered via ex vivo encapsulation into autologous erythrocytes (EDS), or an infusion of erythrocytes prepared using a placebo solution instead of a DSP solution, that are infused into the patient with AT.

	
Autologous whole blood (50 ± 5 mL) to be used for the EDS process will be collected by peripheral venipuncture into heparinized collection tubes.
 
• Group 1: EDS-EP low dose range of ~5-10 mg DSP/infusion: CCI [REDACTED]• Group 2: EDS-EP high dose range of ~14-22 mg DSP/infusion: CCI [REDACTED]• Group 3: Placebo: Patients will be treated with autologous erythrocytes prepared with the EDS process using a placebo solution CCI [REDACTED] 
Study treatment will be administered by IV infusion once per month for 12 consecutive months (6 months initial treatment + 6 months extension treatment; additional blinded unscheduled treatments will be performed in case a patient is willing to be enrolled in the open-label study IEDAT-03-2018, but the study has not yet received IRB/EC approval at the time the patient reaches Visit 15/Month 12; these unscheduled infusions will be started from the time Visit 15/Month 12 should be performed, and continuing until the site has been initiated for the open-label study IEDAT-03-2018 and he/she has been evaluated for eligibility for the study).
 
CCI [REDACTED]

Reference Therapy:
	
For patients randomized to the Placebo group, CCI [REDACTED]

Planned Treatment Duration per Patient
	
The study will consist of a 30-day Screening Period followed by two sequential (each one approximately 180-day long) treatment periods, for a total treatment duration of approximately 360 days. Patients completing the Initial Treatment Period that are doing well on their assigned treatment will have the option of continuing treatment in the Extension Treatment Period. One third of patients randomized to the Placebo group (Group 3) in the initial period that continue in the extension period will continue to receive placebo throughout the treatment

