5.2.4 Extent of Treatment Exposure and Compliance

Unless specified otherwise, extent of exposure and compliance parameters will be summarized for the safety population by treatment received during the initial treatment period, Visits 9 to 12 (“Month 6 to 9”), and Visits 12 to 15 (“Month 9 to 12”), and by treatment scheme received (the seven schemes assigned at randomization) for the total study. Table 5 illustrates how subjects will be allocated to treatment during different periods of the study, under the assumption that no subjects drop out.

Table 5. Planned Subject Allocation to Treatment During Each Study Period

	EDS-EP Low Dose	EDS-EP High Dose	Placebo	Non- switch Placebo	Visit 9 EDS-EP Low Dose	Visit 9 EDS-EP High Dose	Visit 12 EDS-EP Low Dose	Visit 12 EDS-EP High Dose
Initial Treatment Period	60	60	60					

Visit 9 ("Month 6") to Visit 12 ("Month 9")	60	60		40	10	10		
Visit 12 ("Month 9") to Visit 15 ("Month 12")	60	60		20	10	10	10	10

Note: Table presents number of subjects allocated per treatment per period assuming no subjects drop out.

Duration of Treatment and Number of Infusions

Duration of treatment in the initial treatment period will be calculated in days as the date of the last infusion of study treatment during the initial treatment phase (Visit 9) – date of the first infusion of study treatment + 1. Duration of treatment for Visits 9 to 12 ("Month 6 to 9") will be calculated in days as the Visit 12 infusion date – the Visit 9 infusion date + 1, and the duration of treatment for Visits 12 to 15 ("Month 9 to 12") will be calculated in a similar manner. Total duration of treatment (initial treatment period + extension treatment period) will be calculated in days as the date of last infusion of study treatment – date of the first infusion of study treatment + 1.

Duration of treatment and number of infusions received will be summarized by treatment period using summary statistics for continuous variables. The number and proportion of subjects with duration of treatment longer than 228 days in the initial treatment period will be summarized. The exact loaded dose of dexamethasone in Erydex administered to each subject at each dosing visit will be summarized.

Extent of Exposure

Total monthly treatment exposure is defined as the count of monthly treatments, including missed monthly treatments, from the first monthly treatment to the last monthly treatment.

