- Events with partial onset dates that indicate that the event could be treatment-emergent during the period.
- Events with completely missing onset dates.

For adverse event reporting, subject events will be allocated to the period of last treatment.

For each treatment period and over all periods, an overall summary of the number and percentage of safety population subjects having pre-treatment AEs and TEAEs will be presented by treatment received, along with the total number of TEAEs. This summary will also include the number and percentage of subjects with related TEAEs, serious TEAEs, serious related TEAEs, TEAEs leading to discontinuation, and TEAEs leading to death. Only subjects treated during the period of interest will be included in the denominator for percentages. For the summarization of AEs over all periods, treatments summarized will include EDS-EP low dose and high dose groups, non-switch placebo, placebo pre-switch, and each active treatment post-switch; placebo subjects who switch to active treatment will have only adverse events emergent during active treatment summarized.

TEAEs will also be summarized as the number and percentage of safety population subjects treated during the period (or the study overall) having any event and any event by MedDRA system organ class and preferred term. For each subject, multiple occurrences of the same event will be counted once within a system organ class and preferred term. Summaries will be prepared for the following types of events:

- TEAEs
- Related TEAEs
- Serious TEAEs
- Related Serious TEAEs
- Potentially steroid-related TEAEs
 - Low bone mineral density
 - Low CD4 count
 - Itching
 - Osteopenia
 - Osteoporosis
 - Weight gain
 - Cortisol suppression
 - Glaucoma
 - Stunt growth
 - Infections
 - Hyperglycemia
- TEAEs indicative of adrenal insufficiency per Protocol Appendix 12 and monitored by a data safety monitoring board
- TEAEs leading to discontinuation
- TEAEs leading to death
- TEAEs by maximum severity
- TEAEs by worst relationship

This summarization will be repeated for Continuous Exposure 2 subjects, and for subjects whose treatment was ended due to COVID-19.

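### The entire-study adverse event tables set crude percentages for the shorter pre-switch and post-switch columns beside 12-month columns, with no exposure adjustment

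*SAP*

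**What the plan says.** SAP 5.4.1 (Adverse Events) plans summaries for each treatment period and over all periods. For the over-all-periods summary, "treatments summarized will include EDS-EP low dose and high dose groups, non-switch placebo, placebo pre-switch, and each active treatment post-switch". The system organ class and preferred term tables give the "number and percentage of safety population subjects treated during the period (or the study overall) having any event". Each subject contributes once: "multiple occurrences of the same event will be counted once within a system organ class and preferred term". The denominator is a count of people: "Only subjects treated during the period of interest will be included in the denominator for percentages".

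The design fixes how long each column is observed. The Protocol synopsis describes the two treatment periods "for a total treatment duration of approximately 360 days". It then staggers the placebo switch: "Following 6 months of treatment, one third of the originally randomized placebo patients will be re-randomized to treatment with EDS-EP" and "After 9 months of treatment, one third of the originally randomized placebo patients will be re-randomized to treatment with EDS-EP". SAP 5.2.4, Table 5 gives the planned numbers, with the note "Table presents number of subjects allocated per treatment per period assuming no subjects drop out".

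The affected outputs in SAP 6.3.3 are Tables 14.3.1.1.4 to 14.3.1.10.4 (entire study) and the matching .5 tables for Continuous Exposure 2 subjects. SAP 5.2.4 derives duration of treatment in days, but neither 5.4.1 nor the adverse event table list uses it, or any other person-time, as a denominator.

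**The concern.** A percentage of subjects with at least one event is a cumulative incidence, and it rises with time at risk. In the entire-study tables, columns observed for about 12 months stand next to columns observed for roughly half that time or less. If every treatment carried the same event rate, post-switch EDS-EP would look safer than original EDS-EP, and placebo pre-switch would look safer than either 12-month EDS-EP column.

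Long-term safety over up to 12 months is a secondary objective of the extension period (Protocol section 8). Protocol section 7.3 justifies the staggered switch partly by the placebo data it yields for long-term comparison. The entire-study tables are a natural place to look for that comparison, including for serious, steroid-related and adrenal events. A reader who scans across the row could take a difference in follow-up for a difference in safety.

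**Working it through.** **1. Reproduce Table 5.** With 60 placebo patients, 60/3 = 20 switch at Visit 9 (10 to each dose), leaving 40. Half of these, 40/2 = 20, switch at Visit 12 (10 to each dose), leaving 20. This matches SAP Table 5. Enrolment closed at 175 rather than 180, so actual numbers will be slightly smaller.

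**2. Planned exposure per column, no dropout.**

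| Column | Months per subject | Patient-months |
|---|---|---|
| EDS-EP low, EDS-EP high (each) | 12 | 60 × 12 = 720 |
| Non-switch placebo | 12 | 20 × 12 = 240 |
| Placebo pre-switch | 6 or 9, mean 7.5 | 20 × 6 + 20 × 9 = 300 |
| Post-switch, each dose | 6 or 3, mean 4.5 | 10 × 6 + 10 × 3 = 90 |

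**3. Displayed percentage under one common rate.** The documents give no adverse event rate, so a constant hazard, equal in every column, is assumed and a range is shown. With six-month risk r, the hazard is h = −ln(1 − r)/6 and the risk by month m is 1 − exp(−h·m). Mixed columns average their two durations 1:1.

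- r = 50%: the risks at 3, 6, 9 and 12 months are 29.3%, 50.0%, 64.6% and 75.0%. Pre-switch is (50.0 + 64.6)/2 = 57.3%. Post-switch is (50.0 + 29.3)/2 = 39.6%.
- r = 20%: the risks are 10.6%, 20.0%, 28.4% and 36.0%. Pre-switch is (20.0 + 28.4)/2 = 24.2%. Post-switch is (20.0 + 10.6)/2 = 15.3%.
- Rare event, 12-month risk 5%: 5.0% (12 months), 3.2% (pre-switch), 1.9% (post-switch).

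**4. Add the 60-day tail.** SAP 5.4.1 counts events up to 60 days after the last dose in the final period. The twelfth infusion is at Month 11, so the 12-month columns become about 13 months and the post-switch durations about 7 and 4 months. Pre-switch time ends at the switch and is unchanged. At r = 50%:

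- 12-month columns: 1 − 0.5^(13/6) = 77.7%.
- Post-switch: [1 − 0.5^(7/6) + 1 − 0.5^(4/6)]/2 = (55.5 + 37.0)/2 = 46.2%.
- The gap to post-switch goes from 75.0 − 39.6 = 35.4 points to 77.7 − 46.2 = 31.5 points.
- The gap to pre-switch goes from 75.0 − 57.3 = 17.7 points to 77.7 − 57.3 = 20.4 points.

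The tail therefore narrows the post-switch gap, slightly widens the pre-switch gap, and removes neither.

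**5. Check the remedy.** First events divided by person-time to first event estimate h in every column. For r = 50% that is 0.693/6 = 0.1155 per month, or 11.6 per 100 patient-months. For r = 20% it is 0.223/6 = 0.0372, or 3.7 per 100 patient-months. Equal hazards then show as equal rates.

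**The case against.** The case for leaving the tables alone has real substance.

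- **The main contrast is fair.** Original EDS-EP against non-switch placebo is about 12 against 12 months in the same table. That stands. A reader might infer that the entire-study placebo comparison as a whole is biased; the documents do not support this. The small non-switch column is a disclosed design choice.
- **Equal-exposure tables exist.** Every summary is also produced for Periods 1, 2 and 3 (about 6, 3 and 3 months), by treatment received and with only subjects treated in that period in the denominator. This stands as the chief mitigation, but each table covers only part of the year and does not correct the entire-study display.
- **Nothing is tested.** SAP 5.4 plans no statistical comparison of safety data, so no error rate is at stake. Total event counts and exposure are also reported, though neither gives subjects with a first event over time at risk.
- **No 3-month or 9-month column is defined.** The SAP wording separates post-switch columns by dose, not by switch visit. A reader might set 29% against 75% as a column contrast, but those are patient-level extremes; the columns as worded are mixtures.
- **COVID-19 gaps.** A reader might infer that long interruptions remove time unevenly between arms. No figure supports that, and SAP 5.1.3 treats the disruption as random across subjects. SAP 5.4.1 also plans on-dose, off-dose and restart tables for subjects with gaps over 60 days.
- **The pre-switch column may be empty.** The sentence that lists it goes on to restrict switchers to events arising on active treatment. Read literally, that leaves the column with no events. The two statements need reconciling. Even so, the post-switch columns remain affected.

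**Conclusion.** The concern holds for the placebo pre-switch and post-switch EDS-EP columns of the entire-study tables, and only there. With identical rates, a common event (50% six-month risk) would differ by about 18 points between the 12-month and pre-switch columns, and by about 35 points between the 12-month and post-switch columns. At 20% six-month risk the gaps are about 12 and 21 points. For rare events the absolute gap is a few points, although 5.0% against 1.9% is still a ratio of about 2.6.

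These sizes rest on an assumed constant hazard, planned numbers, no dropout, and columns pooled over switch visits. The direction does not depend on the particular hazard, because cumulative incidence cannot fall with longer follow-up. This is a fault of presentation and interpretation. It gives no ground for saying that the plan's safety conclusions are invalid or that the 12-month placebo comparison is distorted. It is worth correcting because the remedy is cheap and the tables invite the misreading.

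**What to change.** In SAP 5.4.1 and the entire-study tables for TEAEs, serious, steroid-related and adrenal events, add two items per column: person-time at risk, and exposure-adjusted incidence. The incidence is subjects with a first event per 100 patient-months (or patient-years), with a 95% confidence interval. At-risk time ends at the first event, at the switch, or 60 days after the last dose, whichever comes first. Off-dose gaps beyond 60 days are excluded, so that the denominator matches the treatment-emergent rule already applied to the numerator. The adrenal summary is named in 5.4.1 but has no numbered table in 6.3.3, so it needs one.

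Show a supplementary column pooling all placebo time up to switch: 240 + 300 = 540 planned patient-months. Keep every crude percentage, including those for Periods 1, 2 and 3, since these give the nominally equal-exposure comparisons. State whether the pre-switch column includes switchers' placebo-time events.

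Add a caution for visit-detected events. Bone mineral density and scheduled post-baseline CD4+ counts are measured only at Months 6 and 12, so a rate over a short post-switch window partly reflects the assessment schedule.

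The cost is SAP wording and modest programming from infusion and event dates already collected; design and data collection do not change. The downside is that a single rate assumes a roughly constant hazard, which may not suit cumulative steroid effects. For that reason the rates should supplement the percentages and not replace them.

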5.4.2 Physical and Neurological Examination

Physical and neurological examinations will be performed at Screening, at Baseline (pre and post infusion) and prior to dosing at each of the monthly infusions (Visit 4 [“Month 1”], Visit 5 [“Month 2”], Visit 6 [“Month 3”] [also post infusion], Visit 7 [“Month 4”], and Visit 8 [“Month 5”]) and at the final visit (Visit 9 [“Month 6”] or at early discontinuation) during the initial treatment period. For subjects continuing in the extension treatment period, physical and neurological examinations will be performed pre- and post-infusion at Visit 9 (“Month 6”) and Visit 12 (“Month 9”), prior to dosing at each of the other monthly infusions (Visit 10 [“Month 7”], Visit 11 [“Month 8”], Visit 13 [“Month 10”], and Visit 14 [“Month 11”]) and at the final visit (Visit 15 [“Month 12”] or at early discontinuation).

If clinically significant abnormal findings are noted at Screening, the examination was to be repeated prior to Baseline. The physical examination will include an examination of general appearance, skin, neck (including thyroid), eyes and ears, nose, mouth, throat, lungs, heart, abdomen, back, lymph nodes, extremities and nervous system. Genital, urinary tract and rectal examinations are not required. The findings will be entered on the Physical Examination section of the CRF.

Physical and neurological examination data will be summarized by treatment period and visit according to the treatment received during the period. Shift tables will be provided for all values and separately for abnormal values (both clinically significant abnormalities and not). Baseline will be defined two ways, as the last assessment prior to the first infusion in the study (Baseline 1), and also as Baseline 1 for non-switch groups and as the last assessment prior to switch for placebo switchers (Baseline 2), and thus summaries will be repeated to reflect the use of each baseline definition.

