	
• Special laboratory tests on the diverted blood sample: HbA1c, CD4+ lymphocytes count, α-fetoprotein, CRP, and RBC antibodies (IgG, IgM, Qualitative Direct Coombs test), only on Months 6 and 12.• Mini-ATM detection on the diverted blood sample, only on Month 6.• Serum pregnancy test (women of childbearing potential) on the diverted blood sample, only Month 6 and Month 12.• Urine pregnancy test will be performed before every infusion for women of childbearing potential.• Assessment of physical development, sexual maturation, and the effect of treatment with dexamethasone on these aspects. Tanner staging of the breasts in pre-menarchal females and of the scrotum in males who have not completed puberty, will be performed at Months 6 and 12. Post-menarchal females and males who have completed puberty will be excluded from this growth analysis.• Hemolysis panel [free plasma hemoglobin, haptoglobin, bilirubin (total and conjugated), LDH] (Months 3, 6 and 9 only)• Bone mineral density [on Months 6 and 12 only]• Assessment of concomitant medications• Assessment of AEs• Blood sample for dexamethasone PK (Months 3 and 6 only) just before the infusion• Upon completion of the EDS process, fill the satellite sample bag with approximately 6 mL of EDS-EP by gravity (approximately 2 mL if no other samples but the ones for sterility culture test will be collected). A 1-mL sterile sample of the EDS-EP will be stored under refrigeration as a "Retention Sample".• Upon completion of the EDS process 5 mL of the EDS from the EryKit_01 bowl at the end of the process will be collected to assess RBC osmotic resistance (in selected centers)• Study treatment administration by IV infusion, once all assessments have been completed.• CCI [REDACTED] 
After completion of the IV infusion of the study treatment the following assessments will be performed:
 
• Physical examination and vital signs 1-2 hr after infusion• Blood sample for dexamethasone PK 1 hr after infusion (Month 3 only)• Free plasma hemoglobin (1 hr post infusion)-(Months 3, 6 and 9 only)• Assessment of concomitant medications• Assessment of AEs 
In case a patient is willing to be enrolled in the open-label study IEDAT-03-2018, but the study has not yet received IRB/EC approval at the time the patient reaches

--	--

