11.5.3 Month 9 (Visit 12)

Pre-infusion

- a) Randomized switch of another one-third of placebo patients to EDS-EP treatment
- b) Physical/neurological examination

- c) Vital signs – including body weight and height in triplicate,
- d) 12-lead standard ECG
- e) Laboratory evaluations on the diverted blood sample, comprising the following tests:
 - i. hematology
 - ii. clinical chemistry
 - iii. urinalysis
- f) Hemolysis panel [free plasma hemoglobin, haptoglobin, bilirubin (total and conjugated), LDH]
- g) Urine pregnancy test will be performed before infusion (for women of childbearing potential)
- h) C-SSRS
- i) ICARS (with video recording)
- j) CGI-C
- k) CGI-S
- l) VABS
- m) EQ-5D-5L
- n) 1 mL blood collected, after blood diversion, for aerobic culture
- o) Autologous blood collection for EDS processing

p) CCI [REDACTED]

[REDACTED]

[REDACTED]

- s) Review of AEs – reported by the patient or observed by the Investigator.
- t) Review of concomitant medication
- u) **Infusion of EDS-EP autologous RBCs.**

Post-infusion

- v) Physical examination
- w) Vital signs
- x) Hemolysis panel [free plasma hemoglobin only, 1 hr post-infusion]

Version 1.0, 09May2015; Version 2.1, 16Nov2015; Version 3.0 (Amend. 1), 01Feb2016; Version 3.1 (Amend. 2), 28Apr2016; Version 3.2 (Amend. 3), 25May2016; Version 4.0 (Amend. 4), 29Nov2016; Version 5.0 (Amend. 5, Site-specific), 20Sep2017; Version 6.0 (Amend. 6), 29Sep2017; Version 7.1 (Amend. 7.1), Final 13 March 2018, Version 8.0 (Amend. 8.0), Final 23 April 2018; Version 10.0 (Amend. 10), Final 16 April 2019; Version 11.0 (Amend. 11), Final 24 Jun 2020

- e) Assessment of physical development, sexual maturation, and the effect of treatment with dexamethasone on these aspects (Tanner scale)
- f) Special laboratory tests on the diverted blood sample: HbA1c, CD4+ lymphocytes count, α -fetoprotein, CRP, and RBC antibodies (IgG, IgM, Qualitative Direct Coombs test)
- g) ICARS (with video recording)
- h) CGI-C
- i) CGI-S
- j) VABS
- k) EQ-5D-5L
- l) C-SSRS
- m) Bone mineral density
- n) Review of AEs – reported by the patient or observed by the Investigator.
- o) Review of concomitant medication

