13.5 Special Laboratory Evaluations

Measurement of selected “special” laboratory parameters has been included in the study to evaluate potential effects of dexamethasone (EDS-EP) treatment (for details on aseptic procedure for blood withdrawal and on blood diversion see “Revised Study Procedures on Sterility Testing for Study IEDAT-02-2015 (ATTeST)”; [Appendix 13](#)). The following special laboratory parameters will be assessed in the study:

- Blood glycosylated hemoglobin (HbA1c, %), CD4+ lymphocytes, α -fetoprotein (not repeated at baseline), C-reactive protein (CRP), and RBC antibodies (IgG, IgM, Qualitative Direct Coombs test) (not repeated at baseline)– to be performed at Screening and Baseline (Day 0) and on Months 6 and 12 (or at early discontinuation).
- Screening for adrenal insufficiency will be performed in all patients, regardless of weight, via early morning (before 8:00 AM) plasma cortisol testing at the following times: (1) during the screening period (prior to randomization), (2) when patients are symptomatic, and (3) when patients are at most risk for adrenal insufficiency and adrenal crisis, such as following discontinuation or interruptions of dexamethasone dosing (i.e., loading failures and following discontinuation of the study drug). If the 8:00 AM cortisol level is below 3-5 $\mu\text{g/dL}$ (depending on assay) regardless of symptoms, or the patient exhibits signs or symptoms of adrenal insufficiency ([Appendix 12](#)) and has a cortisol $<10 \mu\text{g/dL}$, the patient will receive a high dose ACTH stimulation test, regardless of weight, within 24 hours. If the ACTH stimulation test is normal, the patient can be enrolled, or can continue dosing with EDS-EP, after the effects of the ACTH have dissipated (e.g., 30 days after ACTH administered). If the patient fails the ACTH stimulation test they will be excluded or discontinued from the study and referred to a pediatric endocrinologist, with a recommendation to prescribe stress dose steroids.

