13.8 Bone Mineral Density (BMD)

Measurements of BMD will be performed for all patients at Baseline and repeated at 6 and 12 months to assess potential steroid-related changes. Bone mass will be measured in the spine and total body (less the head), following the guidelines provided in the 2013 International Society for Clinical Densitometry Official Pediatric Position ([Gordon et al, 2014](#)). The suggested method for assessing BMD in the study is dual energy x-ray absorptiometry (DXA). The analysis will be performed with Z-scores following the above guidelines. The same method of assessment will be used for each patient throughout the study.

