13.9 Tanner Staging

Assessment of physical development, sexual maturation, and the effect of treatment with dexamethasone on these aspects will be evaluated using the Tanner scale ([Marshall and Tanner 1969, 1970](#)) at Baseline, and 6 and 12 months. The scale defines physical measurements of development in children, adolescents and adults based on external primary and secondary sex characteristics, such as the size of the breast, genitals, testicular volume and development of pubic hair. Due to natural variation, individuals pass through the Tanner stages at different rates, depending in particular on the timing of puberty. Tanner staging of the breasts in pre-menarchal females and of the scrotum in males who have not completed puberty, will be performed. Post-menarchal females and males who have completed puberty will be excluded from this growth analysis.

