5.4.7 Bone Mineral Density

Bone mineral density z-scores will be summarized and analyzed in a manner similar to the standard laboratory evaluations.

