5.4.8 Tanner Staging

The number and percentage of safety population subjects at each Tanner stage will be summarized treatment period and by visit according to treatment received during the period. Summaries will be repeated to reflect the use of Baseline 1 and Baseline 2, as defined in [Section 5.4.2](#).

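### For safety measures taken only at baseline, Month 6 and Month 12, the pre-switch baseline of Month-9 switchers is their Month 6 value, so about half of the interval tabulated under EDS-EP is placebo time

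*SAP*

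**What the plan says.** SAP section 5.4.2 defines two baselines for safety data. Baseline 1 is the last value before the first infusion of the study. Baseline 2 is the same for patients who do not switch, but is taken "as the last assessment prior to switch for placebo switchers (Baseline 2" in the others. Section 5.4.6 applies both to laboratory data, and its Table 7 includes HbA1c and CD4. It calculates change from baseline to each visit and presents results by the treatment received in the period. Section 5.4.8 does the same for Tanner stage: "Summaries will be repeated to reflect the use of Baseline 1 and Baseline 2". For BMD, section 5.4.7 gives only a cross-reference: "Bone mineral density z-scores will be summarized and analyzed in a manner similar to the standard laboratory evaluations".

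One third of the placebo group switches at Month 6. At Month 9 the protocol (section 11.5.3) lists: "Randomized switch of another one-third of placebo patients to EDS-EP treatment".

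The measurement schedule is as follows.

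- **BMD** (protocol 13.8): "Measurements of BMD will be performed for all patients at Baseline and repeated at 6 and 12 months". The synopsis visit list for Months 3, 6, 9 and 12 agrees: "Bone mineral density [on Months 6 and 12 only".
- **Tanner stage** (protocol 13.9): "at Baseline, and 6 and 12 months".
- **HbA1c, CD4, alpha-fetoprotein, CRP and RBC antibodies** (protocol 13.5): "to be performed at Screening and Baseline (Day 0) and on Months 6 and 12 (or at early discontinuation". Alpha-fetoprotein and RBC antibodies are not repeated at baseline.

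The Month 9 visit list in protocol section 11.5.3 and flow chart Table 2B show none of these at Month 9.

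**The concern.** Baseline 2 exists so that a switcher's change can be read as change after starting EDS-EP. That works where the measure is taken just before the first active infusion. Routine laboratory tests, ECG, vital signs, and physical and neurological examinations are all done at Month 9, so they are sound. For the measures listed above, a Month-9 switcher's last scheduled pre-switch value is three months old at the switch, and the SAP has no rule for that case.

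SAP Tables 14.3.7.1.3, 14.3.7.2.3 and 14.3.7.3.3 cover special laboratory values, shifts and abnormal shifts for Visits 12 to 15 against the pre-switch baseline. In these patients the interval behind the entries starts at Visit 9. The companion tables for Visits 9 to 12 have no scheduled Month 9 value at all, which suggests that one template was applied without checking the schedule.

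The measures matter for a steroid product. The protocol measures BMD to look for steroid-related change. In the Phase II trial, two patients stopped because of falls in CD4 count judged related to treatment (protocol 7.1.3.1). Long-term safety is a secondary objective of the extension. A reader of these tables would take the entries as change on active treatment.

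**Working it through.** **Inputs.** Visit 9, Visit 12 and Visit 15 target days are 180, 270 and 360 (SAP Tables 1 and 2). Infusions are 21 to 28 days apart with a window of +10 days, so intervals run from 21 to 28 + 10 = 38 days (protocol 11.2). The planned placebo group is 60, and 175 patients were enrolled.

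**Reproducing the plan's own figures.**
- Longest initial period: 6 × 38 = 228 days, as stated in SAP section 1.3. This supports 38 days as the upper interval.
- Month-9 switchers: 60 × 1/3 = 20, and 20 × 1/2 = 10 per dose, as in SAP Table 5.

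**Share of the Baseline 2 interval spent on placebo.**

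Share = (Visit 12 day − Visit 9 day) / (Visit 15 day − Visit 9 day)

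- Nominal: (270 − 180) / (360 − 180) = 90/180 = 50%. Placebo is infused at Months 6, 7 and 8, and EDS-EP at Months 9, 10 and 11.
- Shortest placebo stretch, longest active stretch: 3 × 21 = 63 and 3 × 38 = 114 days, so 63/177 = 36%.
- The reverse: 114/177 = 64%.
- Early final assessment, with equal intervals: two intervals after the switch gives 3/(3 + 2) = 60%; one gives 3/(3 + 1) = 75%.
- Month-6 switchers: 0%, because their Month 6 value is taken at the switch.

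**Patients affected.** 20 as planned; at 175 enrolled, 175 × 1/3 × 1/3 = 19.4. Both are before dropout.

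**Which outputs are reached.**

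| Measure | Route to Baseline 2 | What is affected |
|---|---|---|
| Special laboratory tests | SAP 5.4.6; Tables 14.3.7.1.3, 14.3.7.2.3, 14.3.7.3.3 | Change and shift |
| Tanner stage | SAP 5.4.8; Table 14.3.15.3 | Baseline stage shown; no change score is planned |
| BMD | Cross-reference in SAP 5.4.7 only; Tables 14.3.9.1 to 14.3.9.3 are not split by baseline | Change and shift, if Baseline 2 is applied |

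**The case against.** The strongest reply is that the tables are not literally wrong. A Month 6 value is the last one before the switch, and a title that says pre-switch baseline is accurate. The summaries are descriptive: SAP section 5.4 rules out statistical comparisons between groups. The randomized comparison through Month 6 and the Month 12 data of the original EDS-EP arms are clean and untouched. A footnote giving the date of the baseline would disclose the problem. The mock shells are in a separate document (SAP section 6); if they follow the columns of SAP Table 5, the two switch groups are already apart.

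Most of this stands as a limit on importance. It does not remove the defect: even in a separate column, six months of follow-up would appear under a three-month period and an EDS-EP dose unless labelled.

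Three stronger readings are tempting, and the documents do not support them.

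- **That half of the reported change is placebo change.** Only half of the interval is. The split of the change is unknown. A drug effect could be diluted by shorter exposure, but protocol section 7.3 describes progressive immune weakening, so a CD4 fall on placebo could equally add to the apparent decline on drug.
- **That pooling the two switch groups understates a drug effect by 25%.** That needs linear accrual, no change on placebo, and a pooling of the two switch groups alone that the SAP nowhere states.
- **That the SAP's list of potentially steroid-related events is distorted.** Low BMD and low CD4 are on it, but as treatment-emergent adverse events assigned by onset and treatment period. They do not use Baseline 2.

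**Conclusion.** The point holds for the special laboratory tests, for the baseline stage shown in the Tanner summaries, and for BMD if Baseline 2 is carried over through SAP section 5.4.7. Following the plan as written gives Month-9 switchers an interval that is nominally 50% placebo time (36% to 64% under permitted visit spacing) under an EDS-EP heading, in about 19 to 20 patients before dropout.

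This assumes the scheduled visits are kept and no extra value exists between Months 6 and 9. An unscheduled CD4 or HbA1c result could give an individual a later baseline. Protocol Appendix 14, on the COVID-19 changes, was not in the text available and could bear on this.

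The fault is mislabelled exposure time in descriptive safety tables. No size or direction of bias can be given, and no efficacy conclusion is affected. It should still be corrected, because the cause is a stated rule and the correction is cheap.

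**What to change.** Add a rule to SAP section 5.4.2 for measures not scheduled at the switch visit. For the special laboratory tests, Tanner stage and BMD:

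- limit the Baseline 2 post-switch summary of change on EDS-EP to Month-6 switchers;
- show Month-9 switchers in a separate column, labelled '3 months placebo + 3 months EDS-EP (baseline = Month 6)', and do not count them as change on EDS-EP;
- state in section 5.4.7 whether Baseline 2 applies to BMD, and align Tables 14.3.9.1 to 14.3.9.3 with the answer.

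No new data are needed. The cost is that the post-switch group for these measures falls from about 20 to about 10 per dose, and several special-laboratory and Tanner table shells have to change.
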